4.2 Exclusion Criteria

- 1. Prior exposure to a bromodomain inhibitor, such as OTX-015 or CPI-0610
- 2. Ongoing systemic infection requiring treatment with antibiotic, antiviral, or antifungal treatment
- 3. Autoimmune hemolytic anemia or autoimmune thrombocytopenia
- 4. Presence of symptomatic or uncontrolled central nervous system or leptomeningeal metastases (Note: Subjects with stable, treated brain metastases are eligible for this study. However, subjects must not have required steroid treatment for their brain metastases within 30 days of Screening.)
- 5. Red blood cell or platelet transfusion within 14 days of Screening blood draw
- 6. Known or suspected allergy to the investigational agent or any agent given in association with this study
- 7. Use of biotin (i.e., Vitamin B7) or supplements containing biotin higher than the daily adequate intake of 30 μg (NIH-ODS 2020). (Note: Subjects who switch from a high dose to a dose of 30 μg/day or less are eligible for study entry.) Use of herbal, alternative, and food supplements (i.e., PC-Spes, Saw Palmetto, St. John's Wort, etc.) and probiotics must be discontinued before treatment start. Daily multi-vitamin (provided it does not contain biotin >30 μg/day), calcium, and Vitamin D are permitted.

- 8. Use of strong inhibitors and inducers of CYP3A4 and 2C8 (Appendix 2)
- 9. Clinically significant cardiac disease, defined as any of the following:
 - Clinically significant cardiac arrhythmias including bradyarrhythmias and/or subjects
 who require anti-arrhythmic therapy (excluding beta blockers or digoxin). Subjects with
 controlled atrial fibrillation are not excluded.
 - Congenital long QT syndrome or subjects taking concomitant medications known to
 prolong the QT interval (drugs with a low risk of QTc prolongation that are needed for
 infection control or nausea may be permitted with approval from the Medical Monitor).
 A list of drugs known to prolong the QT interval and risk of Torsades de pointes can be
 found in Appendix 4.
 - QT interval corrected using Fridericia's equation (QTcF) ≥470 msec at Screening (based on average of triplicate electrocardiograms (ECGs) at baseline)
 - If the QTc is prolonged in a subject with a pacemaker or bundle branch block, the subject may be enrolled in the study if confirmed by the Medical Monitor
 - History of clinically significant cardiac disease or congestive heart failure >New York Heart Association Class II. Subjects must not have unstable angina (anginal symptoms at rest) or new-onset angina within the last 3 months or myocardial infarction within the past 6 months.
 - Uncontrolled hypertension, defined as systolic blood pressure >160 mmHg or diastolic blood pressure >100 mmHg that has been confirmed by 2 successive measurements despite optimal medical management
 - Arterial or venous thrombotic or embolic events such as cerebrovascular accident (including transient ischemic attacks), deep vein thrombosis, or pulmonary embolism within the 3 months before start of study medication (except for adequately treated catheter-related venous thrombosis occurring >1 month before the start of study medication)
- 10. Inability to take oral medication or significant nausea and vomiting, malabsorption, or significant small bowel resection that, in the opinion of the Investigator, would preclude adequate absorption
- 11. Poorly controlled known Type 2 diabetes with HbA1C >7.5%
- 12. Non-healing wound, ulcer, or bone fracture
- 13. Infection with HIV-1 or HIV-2. **Exception:** subjects with well-controlled HIV (e.g., CD4 > 350/mm³ and undetectable viral load) are eligible.

- 14. Current active liver disease from any cause, including hepatitis A (hepatitis A virus immunoglobulin M positive), hepatitis B (hepatitis B virus [HBV] surface antigen positive), or hepatitis C (hepatitis C virus [HCV] antibody positive, confirmed by HCV ribonucleic acid). Subjects with HCV with undetectable virus after treatment are eligible. Subjects with a prior history of HBV are eligible if quantitative PCR for HBV DNA is negative. Note that elevated levels of biotin may interfere with viral serology testing.
- 15. Active known second malignancy with the exception of any of the following:
 - Adequately treated basal cell carcinoma, squamous cell carcinoma of the skin, or in situ cervical cancer
 - Adequately treated Stage I cancer from which the subject is currently in remission and has been in remission for ≥2 years
 - Any other cancer from which the subject has been disease-free for ≥ 3 years
- 16. Major surgery or significant traumatic injury within 28 days prior to Cycle 1 Day 1
- 17. Hospitalization for subacute bowel obstruction within 28 days prior to Cycle 1 Day 1
- 18. Receipt of anti-cancer therapy prior to Cycle 1 Day 1:
 - Chemotherapy, radiation therapy, or small molecule anti-cancer therapy for the treatment of cancer within 14 days or 5 half-lives (whichever is shorter) of Cycle 1 Day 1
 - Immune therapy or other biologic therapy (e.g., monoclonal antibodies, antibody-drug conjugates) for the treatment of cancer within 21 days or 5 half-lives (whichever is shorter) of Cycle 1 Day 1

Subjects can receive a stable dose of bisphosphonates for bone metastases, before and during the study as long as these were started at least 28 days prior to treatment with study drug.

- 19. Subject is participating in any other therapeutic clinical study (observational or registry studies are allowed).
- 20. Subjects who are pregnant or breast-feeding
- 21. Presence of any other medical, psychological, familial, sociological, or geographic condition potentially hampering compliance with the study protocol or would interfere with the study endpoints or the subject's ability to participate.

4.2.1 Effective Methods of Contraception

If sexually active, women of child bearing potential must agree to use a highly effective method of contraception (a contraception method with a failure rate <1% per year) and 1 additional barrier method from the time of the negative pregnancy test to 90 days (for subjects in the US) or 6 months (for subjects in Canada) after the last dose of study drug.

Barrier/Intrauterine Methods	Hormonal Methods
Male or female condom with or without spermicide	Implants ^a
Cap, diaphragm, or sponge each with spermicide	Hormone shot or injection ^a
Copper T intrauterine device or levonorgestrel-releasing	Combined pill ^a
intrauterine system (e.g., Mirena®) ^a	Patch ^a

^a Highly effective (failure rate of <1% per year).

5.0 STUDY TREATMENT

5.1 Investigational Product

5.1.1 PLX2853

PLX2853 is formulated as 20 mg strength tablets for oral use. The active drug substance is PLX2853, with additional excipients of hypromellose acetate succinate, copovidone, microcrystalline cellulose, mannitol, croscarmellose sodium, silicon dioxide, sodium stearyl fumarate, sodium bicarbonate, and poloxamer. The drug product presentation is a white to off-white solid tablet. The tablets are embossed with "PLX" on one side.

5.1.2 Carboplatin

Carboplatin is supplied as a sterile, pyrogen-free 10 mg/mL aqueous solution of carboplatin, USP for injection.

The NCCN 2018 recommendations should be used for carboplatin dosing as follows:

The Calvert equation should be applied to calculate dosage using a target AUC in mg \bullet min/mL: Carboplatin dose (mg) = (target AUC) × (GFR + 25)

Target AUC will be 5 mg•min/mL. With the Calvert equation, the total dose of carboplatin is calculated in mg not mg/m². The GFR should be estimated by calculated creatinine clearance (CrCl) using the Cockcroft-Gault equation:

CrCl (male; mL/min) =
$$\frac{(140 - age) \times (weight in kg)}{72 \times serum creatinine (mg/dL)}$$

$$CrCl$$
 (female; mL/min) = $0.85 \times CrCl$ (male)

The dose of carboplatin for desired exposure (AUC) should be capped to avoid potential toxicity due to overdosing. The maximum dose is based on a GFR estimate that is capped at 125 mL/min for subjects with normal renal function. Based on the Calvert equation, the maximum doses can be calculated as follows:

Maximum carboplatin dose (mg) = Target AUC (mg•min/mL) × (125 mL/min + 25)

```
For a target AUC = 5, the maximum dose is 5 \times 150 = 750 mg
For a target AUC = 4, the maximum dose is 4 \times 150 = 600 mg
```

For overweight or obese subjects (body mass index $\ge 25 \text{ kg/m}^2$), consider using an adjusted body weight:

Adjusted body weight (kg) = ideal body weight (IBW) + $0.4 \times$ (total body weight – IBW)

For subjects with abnormally low serum creatinine, including elderly or cachectic subjects, consider using a minimum creatinine of 0.7 mg/dL to avoid overestimation of CrCl.

Once the initial dose of carboplatin is calculated, it does not need to be recalculated for subsequent cycles unless the subject is experiencing toxicity and requires dose modification to a lower dose of carboplatin.

5.2 Study Drug Administration

5.2.1 PLX2853 Administration

PLX2853 should be dosed orally with water using a tablet formulation as defined for each cohort. Subjects should fast for at least 2 hours before and 1 hour after taking PLX2853, except for PK collection days when subjects should fast for at least 8 hours (10 hours on fed dosing day for the optional Food Effect sub-study) before taking PLX2853 (see Section 5.2.3). During the fasting period, subjects may eat a low-fat snack (e.g., crackers, dry toast, etc.) if they experience gastrointestinal symptoms (e.g., nausea, vomiting, etc.) following dosing. PLX2853 should be taken at approximately the same time each day. PLX2853 should be swallowed whole and not crushed, chewed, or dissolved in water. A dosing period of up to 30 minutes is permissible if required by the number of tablets to be taken or as convenient for the subject. Missed doses (generally outside of a 2-hour dosing window for BID dosing and a 5-hour dosing window for QD dosing) should be skipped and not administered as a double dose at the next administration. Subjects who omit their dose should be instructed NOT to make up that dose. Doses that are vomited should not be replaced.

Subjects will be treated with PLX2853 for 28-day cycles. Guidance for dose modification is in Section 6.2.

5.2.2 Carboplatin Administration

For subjects enrolled to the Phase 1b/2a PLX2853 + carboplatin cohorts, carboplatin will be administered intravenously using a target AUC of 5 mg•min/mL on Day 1 of each 28-day treatment cycle per the label. Carboplatin should be administered at least 2 hours after PLX2853 dosing. Prophylaxis for hypersensitivity reaction and skin testing should be considered per institutional standard of care for subjects who have received prior platinum-based regimens. Details on carboplatin dosage calculation is in Section 5.1.2. Guidance for dose modification is in Section 6.2.

5.2.3 Dosing on Pharmacokinetic Sample Collection Days

Subjects should be instructed *not* to take their morning dose of PLX2853 at home before the clinic visit. The time of dosing will be recorded in the clinic. On PK days where a full PK profile is collected (e.g., C1D-3 or C1D-4 (as applicable) C1D1, C1D15), subjects should fast at least 8 hours (10 hours on fed dosing day for the optional Food Effect sub-study) before dose administration and 1 hour (4 hours on fed dosing day for the optional Food Effect sub-study)

after administration of PLX2853. On other PK sample collection days, subject should fast for 2 hours prior to their visit.

5.2.4 Effect of Food on PLX2853

In order to obtain more complete information on the PK profile of PLX2853, PK sampling will be performed in an optional Food Effect sub-study in the Phase 2a monotherapy cohort following a single dose of PLX2853 given 3 or 4 days prior to the start of continuous dosing. Food effect will be examined between test (fed state, Day -4 or -3) and reference (fasted state, Cycle 1 Day 1) treatments using a 1-way crossover design. On Day -4 or -3 following an overnight fast of at least 10 hours, subjects should start the recommended low-fat meal before administration of the drug product and complete the meal in 30 minutes or less. A single dose of PLX2853 should be taken with 8 ounces (240 mL) of water and within 30 minutes after the low-fat meal. No food is allowed for at least 4 hours after the dose.

The low-fat test meal should be approximately 400–500 calories, with approximated 25% of total caloric content coming from fats. An example low-fat test meal is 8 ounces of milk (1% fat), 1 boiled egg, and 1 packet flavored instant oatmeal made with water. A comparable meal may be substituted as long as it contains a similar amount of calories and % fat. The test meal, start and completion time of consumption of the meal, and the proportion consumed by the patient will be recorded on a case report form (CRF). On Day -4 or -3, PK samples will be collected at predose, 0.5, 1, 2, 3, and 5 hours postdose. Additional labs and safety assessments will be performed as specified in the Schedule of Events (Synopsis Table 1).

On C1D1 subjects should fast at least 8 hours before dose administration and 1 hour after dose administration. All labs and safety assessments specified on C1D1 in the Schedule of Events (Synopsis Table 1) must be completed on C1D1.

The Day -4 or -3 (test) and Day 1 (reference) exposures will be compared. The CI₉₀ of the ratio of the test treatment (fed) relative to the reference treatment (fasted) will be obtained. No food effect will be confirmed if the CI₉₀ falls between the 80% to 125% interval following the 2-sided test procedure.

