The drug-drug interaction potential of PLX2853 was further evaluated by measurement of CYP inhibition using recombinant enzymes and CYP induction potential in human hepatocytes. Studies have also been conducted to assess the potential of PLX2853 as an inhibitor of human breast cancer resistance protein (BCRP), P-glycoprotein (P-gp), organic anion transporter (OAT)1, OAT3, OCT2, organic anion transporting polypeptide (OATP)1B1, and OATP1B3 mediated transport in polarized monolayer of Madin-Darby canine kidney II cells. PLX2853 demonstrated no potential to cause direct or time-dependent inhibition CYP1A2, 2B6, 2C8, 2C9, 2C19, 2D6, and 3A4. PLX2853 did not induce any of the respective isoforms of CYP1A, CYP2B, and CYP3A genes at all the concentrations tested in human, monkey, dog, and rat hepatocytes except CYP3A in monkey (34% to 49% of the positive control). Compared to vehicle control, PLX2853 at 10 μM inhibited OCT2, OATP1B1, OATP1B3, BCRP, and P-gp mediated transport by 24.4%, 82.4%, 50.7%, 37.2%, and 48.8%, respectively. Considering the plasma protein binding of PLX2853 (96.1% in human), the plasma concentration to achieve 10 μM free fraction is >250 μM, well beyond the anticipated in vivo exposures. Collectively, these results suggest that the risk of in vivo drug-drug interactions is low for PLX2853.

The food effect on the PK of PLX2853 was evaluated following a single oral dose to male beagle dogs under fasted or fed (high fat diet) conditions. This was a single-dose, 2-period cross-over study where each group received a 40 mg oral dose of PLX2853 (two 20 mg strength tablets) while either fasted or fed and then received the alternate treatment (fasted or fed) following a washout period of 4 days (96 hours) between doses.

Dogs receiving the high fat diet had a significant reduction in exposure of PLX2853. The mean peak concentration (C_{max}) values were 903 and 4870 ng/mL for fed and fasted groups,

respectively. The mean AUC₀₋₂₄ values were 3280 and 14,100 ng•hr/mL for fed vs fasted groups, respectively. The geometric mean ratios (fed/fasted) with the calculated 90% confidence intervals (CI₉₀) for the ratios for C_{max} , AUC₀₋₂₄, and AUC_{0- ∞} were 17.72% (11.71% to 26.81%), and 25.15% (18.34% to 34.548%), and 25.82% (18.92% to 35.24%), respectively.

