1.8 Previous Human Experience

1.8.1 Interim Results of Study PLX124-01

As of 22 March 2021, 46 subjects were enrolled and treated at doses ranging from 5 to 120 mg/day, all in the dose escalation portion of Study PLX124-01 as an ongoing study of PLX2853 in subjects with advanced malignancies and were included in the PK populations. Cohort 1 (3 subjects), Cohort 2 (3 subjects), Cohort 3 (4 subjects), Cohort 4 (3 subjects), Cohort 5 (4 subjects), and Cohort 6 (3 subjects) have been dosed at 5, 10, 20, 40, 80, and 120 mg/day PLX2853, respectively, all with the 5 mg strength tablets. Cohort 7 (9 subjects), Cohort 8 (6 subjects), Cohort 9 (4 subjects), and Cohort 10 (6 subjects) have been dosed at 120 mg QD, 40 mg BID (80 mg total/day), 60 mg BID (120 mg total/daily), and 100 mg QD PLX2853, respectively, all with the 20 mg strength tablets. The total number of subjects in Study PLX124-01 with PK data and included in the PK analysis is 45 subjects.

The Day 1 and Day 15 geometric mean PK parameters are summarized in Table 4. After oral administration up to 120 mg/day PLX2853, rapid absorption was observed with median T_{max} values ranging from 0.5 to 2 hour. Dose-dependent increases in the geometric mean AUC₀₋₂₄ values were observed on Day 1 and Day 15 (steady-state). No significant accumulation of PLX2853 was observed, which is consistent with the short terminal T_{1/2} observed on Day 1 with values <3 hours. Subjects enrolled in Cohorts 1–6 were administered the 5 mg strength tablets. As dose escalation continued, high pill burden increasingly became a challenge for the subjects, which prompted the development of the 20 mg strength tablet. Subjects enrolled in Cohorts 7–10 were administered the 20 mg strength tablets. The Day 1 and Day 15 PK for the 20 mg strength tablets were compared to those for the 5 mg strength tablets at the 120 mg/day dose (Cohorts 6 and 7). The Day 1 exposures (AUC₀₋₂₄) are comparable between the 2 tablet formulations. Because of the small sample size, the statistical significance of the difference could not be assessed.

Table 4: Study PLX124-01: Geometric Means of Pharmacokinetic Parameters at Day 1 and Day 15 (Steady-state) After Oral Administration of 5, 10, 20, 40, 80, 120, and 120 (20 mg strength tablet) mg/day PLX2853 to Solid Tumor Patients

			Geometric Mean b								
				Day 1			Day 15				Accumu-

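### The food-effect comparison restricts food for 4 hours after the fed dose but only 1 hour after the fasted reference dose, which can pull the ratio modestly toward no effect

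*Combined protocol and SAP*

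**What the plan says.** Section 5.2.4 sets up a one-way crossover. The test is a single dose after a low-fat meal on Day -4 or -3, and the reference is the C1D1 dose, which the section labels as fasted.

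- Fed day, after the dose: "No food is allowed for at least 4 hours after the dose".
- Reference day: "On C1D1 subjects should fast at least 8 hours before dose administration and 1 hour after dose administration".
- Fed-day sampling: "PK samples will be collected at predose, 0.5, 1, 2, 3, and 5 hours postdose". Synopsis Table 1 gives the same times for C1D1.
- Decision rule: "No food effect will be confirmed if the CI₉₀ falls between the 80% to 125% interval following the 2-sided test procedure".

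Section 5.2.3 repeats the split, giving the post-dose fast as "1 hour (4 hours on fed dosing day for the optional Food Effect sub-study"). So do the synopsis text on the test product and the fasting footnote to Synopsis Table 1. No section gives sub-study subjects a longer post-dose fast on C1D1.

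The test meal is specified by calories and fat content, and the amount eaten is recorded on a CRF. Nothing similar is specified for food taken after the reference dose. Section 5.2.1, the synopsis and the Synopsis Table 1 footnote also allow a low-fat snack during the fasting period for gastrointestinal symptoms after dosing. Read together with the 4-hour ban in section 5.2.4, this leaves it unclear what a subject may eat on the fed day.

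**The concern.** A food-effect ratio is interpretable when the test meal is the main difference between the two periods. Here the post-dose food rules differ as well, and the looser rule falls on the period labelled fasted.

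Three facts make this relevant. Absorption is described as limited by dissolution rate (section 1.5.2), so it need not be complete within an hour. Median Tmax in Study PLX124-01 is reported with "values ranging from 0.5 to 2 hour", and being medians these leave room for individual subjects to peak later. There is also a reason to suspect that food matters: "Dogs receiving the high fat diet had a significant reduction in exposure of PLX2853", with fed/fasted geometric mean ratios of 17.72% for Cmax and 25.15% for AUC0-24.

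If food taken after 1 hour lowers what remains to be absorbed, reference exposure falls and fed/fasted rises toward 1. If food raises exposure, the ratio falls toward 1. Either way the shift favours the conclusion being tested. It cannot be removed at analysis, because eating after the reference dose is neither standardised nor specified for recording.

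**Working it through.** **No figure to reproduce.** The documents give no sample size, within-subject variability or power for the sub-study. What follows illustrates the size of the bias under stated assumptions.

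**Inputs from the documents**

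- Day 1 median Tmax at 80 mg once daily: 1.0 h in all three cohorts (Table 4 cohort 5; Table 5 cohorts 3 and 4).
- Day 1 half-life in those cohorts: 1.87, 2.07 and 1.95 h. Cohort 4 of Table 5 (1.95 h) used the 20 mg tablet that this study uses.
- Later peaks: at 100 mg once daily, median Tmax is 1.5 h on Day 1 and 2 h on Day 15 (Table 4 cohort 10).
- Longest half-life in Table 4: 4.32 h (120 mg, Day 15, N = 3).

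**Assumptions, not in the documents**

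- One compartment with first-order absorption.
- The subject eats at 1 h.
- That meal reduces the part of the dose still unabsorbed by the same proportion as the test meal reduces the whole dose.

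**Formulas**

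- ke = ln 2 / T½, and ka is solved from Tmax = ln(ka/ke) / (ka − ke).
- Share unabsorbed at 1 h: u = exp(−ka × 1).
- Observed AUC ratio = R / (1 − u × (1 − R)), where R is the true ratio.

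**Results with T½ = 1.95 h (ke = 0.355 per hour)**

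| Tmax | ka | u at 1 h | true 0.75 appears as | true 0.25 appears as |
|---|---|---|---|---|
| 0.5 h | 6.01 | 0.2% | 0.75 | 0.25 |
| 1 h | 2.16 | 12% | 0.77 | 0.27 |
| 1.5 h | 1.12 | 33% | 0.82 | 0.33 |
| 2 h | 0.68 | 51% | 0.86 | 0.40 |

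For example, at Tmax 1 h: 0.75 / (1 − 0.12 × 0.25) = 0.75 / 0.97 = 0.77.

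**Range over half-lives 1.87 to 4.32 h.** At Tmax 1 h, 4% to 12% is unabsorbed and a true 0.75 appears as 0.76 to 0.77. At Tmax 2 h, 32% to 52% is unabsorbed and it appears as 0.75 / (1 − 0.32 × 0.25) = 0.82 to 0.75 / (1 − 0.52 × 0.25) = 0.86.

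**Crossing the limit.** With T½ = 1.95 h, the true ratio that would show as exactly 0.80 is 0.78 at Tmax 1 h, 0.73 at 1.5 h and 0.66 at 2 h.

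**If the two windows matched.** For illustration, had the reference also been protected for 4 h, the share unabsorbed when eating began would be about 0% at Tmax 1 h and 7% at Tmax 2 h (T½ = 1.95 h), against 12% and 51% at 1 h. Most of the bias would go.

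**Cmax.** A meal after 1 h can lower Cmax only in a subject whose peak comes after 1 h.

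**The case against.** The strongest reply is that this does not matter at the study dose. Every 80 mg once-daily cohort has a Day 1 median Tmax of 1.0 h, and section 1.8.1 describes elimination as "consistent with the short terminal T_{1/2} observed on Day 1 with values <3 hours". A true 0.75 then appears as 0.77. A point estimate of 0.77 cannot have its whole 90% interval inside 80% to 125%, so the decision is unchanged. This stands for the typical subject. It does not cover late absorbers, or true ratios close enough to a limit for a small shift to count.

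The dog data are also weaker support than they look. The dogs received a high-fat diet and the trial uses a low-fat meal, so no human food effect is established. An AUC effect as large as in the dogs, 0.25, would appear as 0.27 at Tmax 1 h and about 0.40 at Tmax 2 h, and would plainly fail the rule. That stands too.

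A third reply is that the 1-hour window matches routine dosing in section 5.2.1 and the C1D1 profile of all other subjects, so the reference represents the drug taken as instructed. That would be a legitimate comparison, but the protocol does not state it and instead labels the reference as fasted.

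Finally, the sub-study is optional, has no stated size, and is not named among the objectives or endpoints. That limits the severity of the point but leaves the asymmetry in place.

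**Conclusion.** The point holds as a minor design weakness. The post-dose food rules differ between test and reference, the difference recurs in several places and is corrected nowhere, and any resulting bias favours a finding of no food effect, provided that a later meal acts in the same direction as the test meal. The likely size is small: a true AUC ratio of 0.75 read as about 0.77 at Tmax 1 h, and as 0.82 to 0.86 only for subjects with Tmax near 2 h. These figures rest on the one-compartment model, on the subject eating at 1 h, and on the assumed equal 25% loss. The documents establish none of these.

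A reader might infer two stronger things. The first is that the bias could hide a 25% loss completely. That needs a 2-hour Tmax, which no 80 mg once-daily cohort shows as its Day 1 median, together with a later meal costing about twice as much as the test meal, for which the documents give no basis. The second is that the 10-hour and 8-hour pre-dose fasts are a further imbalance. They are not comparable: the 10-hour fast precedes the test meal, and the fed dose follows that meal.

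**What to change.** Reconcile section 5.2.4 with section 5.2.3, the synopsis text and the Synopsis Table 1 footnote. For Food Effect sub-study subjects only, the same post-dose food restriction, including the snack allowance, should apply on the fed day and on C1D1. The length of the window is for the sponsor to choose; what matters for the comparison is that it is the same on both days. Record on the CRF any food taken during the 5-hour sampling period on both days.

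If the sponsor prefers to keep the current windows, the protocol should say that the comparison is fed dosing versus routine dosing, and limit the conclusion to that.

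The cost is a sentence or two of protocol text and a short CRF entry. The downside is possibly a few more hours without food on a day when these subjects are already in clinic for sampling. Routine dosing and other subjects are unaffected.
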